# Nicotine toxicity

There are minimal risks associated with wearing a nicotine patch including skin irritation, dizziness, lightheadedness, increased heart rate or blood pressure, nausea or vomiting. Despite this low risk, side effects from the combination of NRT and *ad lib* smoking may occur. Rare side effects associated with nicotine toxicity may include: dizziness, lightheadedness, nausea, vomiting, excessive saliva, stomach pain, sweating, headache, dizziness, confusion, weakness, fainting, difficulty breathing, seizures, rapid/weak/ irregular heartbeat, blurred vision, diarrhea, and hearing problems. In previous trials of pre-treatment with 21mg/day nicotine patch there was no evidence of nicotine toxicity even among those smoking regular brand cigarettes (Rose, Behm, Westman, & Kukovich, 2006). In addition, there has been no evidence of serious nicotine toxicity associated with the tailored dose of nicotine patch therapy despite using nicotine patch dosages up to 44 mg/24 hours. Others have used dosages of up to 63 mg/24 hours in smokers without signs of nicotine toxicity.

## Bupropion

Consistent with standard clinical care for smoking cessation pharmacotherapy, all participants who have no contraindications or are medically cleared will be offered bupropion to assist in the quit attempt. Participants with a history of renal failure, hepatitis, cirrhosis, non-alcoholic fatty liver disease, or liver cancer will not be offered

bupropion as part of this study. Since the efficacy of bupropion is well established, we proposed this procedure for each participant to maximize best practices. Beginning one week prior to their quit date, given that they are medically eligible, participants will be prescribed bupropion SR 150 mg to be taken on days 1-3 with an increase to 300 mg beginning on day 4. Participants will continue to receive bupropion until 6 months after their quit date, when they will attend the final study session. These participants may consult their psychiatrist or primary care provider to determine whether they will continue to take bupropion, but this medication will no longer be prescribed through the study after the 6 month follow-up visit. Participants who decline bupropion will remain eligible to complete the study.

## Relapse

All participants will complete the intervention protocol, regardless of smoking relapse. Participants who relapse will have the option of completing the intervention so they can continue to apply smoking cessation skills to subsequent quit attempts. Once the intervention and smoking protocol is completed, participants who relapse will be encouraged to make additional quit attempts until the end of the study at the 6-month follow-up appointment. Relapse will be defined as smoking at least 5 cigarettes a day for 3 consecutive days.

In the follow-up session, if a participant reports an inability to attain or maintain abstinence, we will utilize the Timeline Followback (TLFB) method, which was designed by National Institute on Alcohol Abuse and Alcoholism (NIAAA) to retrospectively evaluate substance use. In this interview, which will last approximately 15 minutes, participants will provide retrospective estimates of their smoking behavior over the time period since their participation. This information will be used to evaluate smoking rates post-quit and relapse incidence among the sample.

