### **Ecological Momentary Assessment**

Participants will monitor smoking for a total of three weeks: the first week of treatment, the first week of the quit attempt, and the first week following the end of treatment. Participants will be paid \$25 per week for monitoring. Participants will also have the opportunity to earn an extra \$25 per week in incentive pay for returning fully completed electronic diaries. During the monitoring period, participants will record any smoking lapses on the electronic diary (ED), immediately after smoking. Smoking lapse assessments will be accompanied by a "situational assessment" including situation,

activity, smoking craving, mood, and PTSD symptoms. In addition, participants will complete situational assessments on at least five occasions per day selected at random by the ED. Random occasion assessments will be stratified every 2.5 hours. The timing of these assessments will be random with the constraint that no prompts will be given for 10 minutes after a cigarette entry.

Prompting will cover all waking hours. When the diary is not completed, up to 3 reminder signals will be emitted at 1-minute intervals and then the diary program will become inaccessible until the next scheduled occurrence. Smokers will be instructed to stop what they are doing when they hear the signal or plan to smoke a cigarette and complete a diary record, which will take about 1 minute. They will be told to ignore any signal that occurs during an incompatible activity (e.g., driving). To increase adherence, participants will be allowed to suspend prompting when responding would be too costly (e.g., church, driving). In previous research using similar methodology, participants suspended prompting only 2 times per week. Additionally, participants will be able to delay an assessment with a 5-minute delay function. Daily start and stop times will be programmed individually according to each participant's usual sleep pattern and entries will be time-stamped.

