#### Intervention Protocol

If screened potential participants are deemed eligible to participate in the study, participants will be randomized to participate in either a 12-session CPT-C with concurrent smoking cessation treatment or a smoking cessation treatment including 6 individual smoking counseling sessions, to be followed (if desired) by CPT-C six months after the quit date. Both arms of the study will include text messaging to support the quit attempt (smokefree VET), pharmacotherapy for smoking cessation, and brief monthly follow-up phone contacts by therapists to support the quit attempt. The complete randomization sequence will be generated a priori and performed centrally by the study staff.

Although participants will attend a total of 15 sessions for this study, not all study sessions will include therapy. In the CPT-C and smoking condition, participants will receive 12 sessions of combined PTSD and smoking therapy. The first 50 minutes of each session will be devoted to the randomized therapy and the last 25 minutes will be devoted to the manualized integrated smoking cessation treatment by McFall and Saxon (McFall & Saxon, 2005). Sessions 7 through 12 of the treatment sessions will include 50 minutes of the randomized therapy, and brief (five to ten minutes) check-in regarding smoking relapse prevention and/or renewed quit attempts. In the smoking cessation without concurrent CPT-C condition, there will still be 15 total study sessions, with 6

including therapy for smoking cessation and lasting 25 minutes. If, during the course of treatment, a participant is lost to contact, the study coordinator will send an IRB-approved "no-contact letter" to increase the likelihood that we re-establish contact.

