### Assessments After Screening

Prior to each session, participants will complete questionnaires to assess psychiatric symptoms and smoking variables. These include the PTSD checklist (PCL), questions about smoking behavior in the past week, and the Beck Depression Inventory (BDI-II). In the final two sessions, participants will also complete the ASI, QOLI, TRGI, PSQI-A, CAPS, treatment satisfaction, Cook Medley Hostility Scale, e-cigarette use measure, and a question about current non-study psychotherapy. In session 8, participants will complete measures of treatment credibility and expectancy using the Reaction to Treatment Questionnaire (Borkovec & Nau, 1972). At the beginning and end of treatment, therapists will rate their level of allegiance to the therapy they are using with a single question asking "Which treatment do you think leads to better outcomes?" In the final treatment session, participants will also complete measures of SmokeFreeVet usability, and the nicotine dependence stages of change measure. In session 14 (after the final treatment session), participants will be interviewed with the CAPS.

Abstinence and relapse will be monitored by ED entries and at visits 7-14. Participants will provide breath samples for carbon monoxide (CO) analysis at every laboratory visit following their quit date. The first verification of smoking abstinence will occur on the morning following their quit date. Smoking abstinence will be obtained by self-report and verified by comparing CO levels to the level obtained at the baseline visit. The chart below lists the sliding scale of CO values that will be considered validating. At the six month follow-up visit, salivary cotinine will also be used to confirm self-reported

smoking abstinence. The formula in Table 1 below uses the participant's CO reading at the screening visit to determine the threshold that will be considered as confirming smoking abstinence after the quit date for each participant.

Table 1. Carbon Monoxide Thresholds for Validating Smoking Abstinence			
CO SCREENING	AM CO LIMIT		
		AM CO Limit after Overnight	
14-15	15	Abstinence	
16-18	16	AM CO Limit Formula: [14 + (.25 *	
19-21	17	(1.33 * (SCREENCO -14)))]	
22-24	18		
25-27	19		
28-30	20		
31-33	21		
34-36	22		
37-39	23		
40-42	24		
43-45	25		
46-48	26		
49-51	27		
52-54	28		
55-57	29		
58-60	30		
61-63	31		
64-66	32		
67	33		

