Hypothesis 3. The CPT-C and smoking cessation protocol will result in decreased smoking rates, relative to published data on VA smoking cessation usual care. An outcome variable denoting the proportion of subjects abstinent at Week-6 will be regressed on the group proxy and included covariates using standard logistic regression procedures. A secondary analysis will explore cessation rates at the 6-month follow-up.

Hypothesis 4.-The level of PTSD symptom reduction during the intervention will be related to longer latency to relapse. PTSD symptom change scores will be used to evaluate the degree of PTSD symptom reduction. We will fit Cox proportional hazard regression models to the data to evaluate effects of PTSD symptom reduction on the time to relapse.

Hypothesis 5. Exploratory research question: Will use of automated text messaging as an adjunct to smoking cessation be feasible, and will it impact quit rates and symptom severity? This will be evaluated by examining proportion of participants choosing to utilize text messaging, retention rates, and usage rates.

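### After session 14, Hypothesis 4's relapse dates depend on attending session 15 and recalling about 19 weeks; the planned monthly calls should record relapse, and a censoring rule should be stated

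*Combined protocol and SAP*

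**What the plan says.** The Relapse section defines the event: "Relapse will be defined as smoking at least 5 cigarettes a day for 3 consecutive days". Up to session 14 it is followed closely. Assessments After Screening states: "Abstinence and relapse will be monitored by ED entries and at visits 7-14". The diary runs for three separate weeks: "the first week of treatment, the first week of the quit attempt, and the first week following the end of treatment" (Ecological Momentary Assessment).

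After session 14 the Relapse section relies on one retrospective interview: "In the follow-up session, if a participant reports an inability to attain or maintain abstinence, we will utilize the Timeline Followback (TLFB) method". Table 2 places it at session 15, six months after the quit date.

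Both arms also receive "brief monthly follow-up phone contacts by therapists to support the quit attempt" (Intervention Protocol). Support is their only stated purpose, and nothing is said about recording smoking.

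Under Hypothesis 4, Data Analysis and Hypotheses states: "We will fit Cox proportional hazard regression models to the data to evaluate effects of PTSD symptom reduction on the time to relapse". The predictor is described only in these words: "PTSD symptom change scores will be used to evaluate the degree of PTSD symptom reduction". There is no censoring date, no rule for participants who miss session 15, and no sensitivity analysis.

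The plan does expect losses. Recruitment provides for partial payment of those who drop out, CPT-C Post Follow-Up anticipates missed appointments, and Intervention Protocol describes a letter that begins from this situation: "If, during the course of treatment, a participant is lost to contact".

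**The concern.** A time-to-event analysis needs a date for each event and a rule for each person whose event status is unknown. For most of the six months after quitting, the plan supplies dates only through one visit and no rule at all.

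Two things follow. Participants who attend session 15 must date a three-day smoking pattern from memory. Participants who do not attend contribute no later relapse, whether or not they relapsed.

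Default Cox handling would censor the second group at last contact. It would then assume that their later relapse risk equals that of attenders with the same PTSD change. If relapse itself keeps people away, and does so more often among those whose PTSD improved least, the missing events are the ones that Hypothesis 4 predicts, and a real association would look weaker. With no written rule, the handling could also be chosen after the data are seen.

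**Working it through.** **Timeline.** NRT ends 6 weeks after the target quit date (Nicotine Replacement Therapy), and Table 2 puts the end of NRT at session 13. Session 14 is the one-week post-treatment visit (Procedures), so it falls at about 6 + 1 = week 7. Taking session 15 as week 26, the stretch dated only by recall is 26 − 7 = 19 weeks, or 19/26 × 6 = 4.4 months.

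**No figure to reproduce.** The document gives no relapse rate, dropout rate, effect size or power for Hypothesis 4. All rates below are assumptions.

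**Simulation** (200,000 participants per scenario):
- Exponential relapse times, baseline hazard 0.06 per week (median ln 2/0.06 = 11.6 weeks), follow-up to week 26.
- True hazard ratio (HR) 0.70 per SD of PTSD reduction.
- A relapser is lost with probability 20% or 30% at average improvement. The odds of loss fall by a factor of 0.61 or 0.37 per SD of improvement.

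At average improvement, 1 − exp(−0.06 × 7) = 34% relapse by week 7 and 1 − exp(−0.06 × 26) = 79% by week 26. So 34/79 = 43% of relapses fall in the well-monitored period.

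Observed HR:

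| Loss among relapsers | Odds factor per SD | Lost only after week 7, censored at session 14 | Lost only after week 7, censored at relapse | Lost at any time from the quit date, censored at relapse |
|---|---|---|---|---|
| 20% | 0.61 | 0.71 | 0.73 | 0.78 |
| 30% | 0.61 | 0.71-0.72 | 0.75 | 0.82 |
| 30% | 0.37 | 0.74 | 0.79 | 0.95 |

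The third column matches the gap described here. The share of the log HR lost is 1 − ln(0.71)/ln(0.70) = 1 − 0.342/0.357 = 4% at the low end and 1 − ln(0.74)/ln(0.70) = 1 − 0.301/0.357 = 16% at the high end. With a hazard of 0.12 per week, the same column gives 0.70-0.71, because more relapses occur before week 7.

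**Direction under other loss patterns** (true HR 0.60 or 0.75, censored at session 14):
- Random 30% loss, or loss that depends on PTSD response but not on relapse: essentially no bias (0.59-0.60; 0.75).
- Relapsers lost equally at all PTSD levels (50%, against 10% of abstainers): no attenuation (0.58-0.60; 0.73-0.75).
- Poor responders who relapse late lost 50%, all others 10%: 0.60, 0.61, 0.63 and 0.65, or 0.75, 0.76, 0.80 and 0.83, for median relapse at 2, 4, 12 and 26 weeks.
- Good responders who relapse lost 50%, all others 10%, medians of 12-26 weeks: 0.54-0.56; 0.68-0.70, which is away from the null.

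**Counting loss as relapse.** Where only relapsers are lost after week 7, coding them as relapsed four weeks after session 14 returns 0.69-0.71 against a true 0.70. But where the true HR is 1.00 and poor responders leave for reasons unrelated to relapse, the same coding gives 0.90-0.96, while censoring gives 1.00.

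**Scale.** Hypothesis 4 is worded for the CPT-C arm. The Population section gives an enrollment goal of at least 50 and elsewhere a figure of 70. With equal allocation (assumed) that is 25 to 35 people, and with 75% relapsing (assumed) 18.75 to 26.25 events. The standard error of the log HR per SD is about 1/√events, or 0.23 to 0.20. The shift is ln(0.71/0.70) = 0.01 to ln(0.74/0.70) = 0.06.

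**The case against.** The strongest reply is that the bias is hypothetical and small. The documents give no evidence that loss depends jointly on relapse and poor PTSD response, and other patterns give no bias or the opposite bias. The shift is well below the standard error. Relapse is monitored closely through week 7, and the Timeline Followback looks back over the whole period, so it can recover relapses for someone who misses interim visits but attends session 15. All of this stands, and it limits the point to a gap in data collection and specification.

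A reader might infer that the plan censors lost participants as relapse-free. No section says so. Censoring is only the software default, and counting the lost as relapsed is equally open. Because the end point of the change score is undefined, early leavers might even be dropped from the model for lack of a post-treatment score; the PTSD Checklist is completed before each session, so either is possible.

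A reader might also infer a large attenuation, of the order of 0.78 to 0.95. Those values arise only if relapsers disappear during the treatment visits as well and then miss session 15. Intervention Protocol allows for loss during treatment, but that is a different mechanism from missing dates after session 14.

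**Conclusion.** The gap is real and its expected effect is modest. After about week 7, relapses are undated for anyone who misses session 15 and rest on more than four months' recall for those who attend, and no rule covers those lost.

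Under default censoring, the association is attenuated only if poor PTSD responders who relapse are the ones lost. On the assumed rates (true HR 0.70 per SD, hazard 0.06 per week, 20-30% loss among relapsers after week 7), the HR moves to about 0.71-0.74. The documents do not support saying that Hypothesis 4 will be biased toward no effect. Nor is there a case for making loss-equals-relapse the primary coding, since that can create the hypothesised association where none exists.

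The change is still worth making because the contacts that would fill the gap are already planned.

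**What to change.** 1. At each monthly therapist call, in both arms, ask and record whether the protocol's relapse definition (at least 5 cigarettes a day for 3 consecutive days) has been met since the last contact, and on what date. Use these dates in the Hypothesis 4 model with the diary, visits 7-14 and the Timeline Followback.
2. State in the analysis section that participants without a recorded relapse are censored at last documented contact, as the primary handling.
3. Add one sensitivity analysis that counts loss to contact after the quit date as relapse at the first missed contact.

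Cost: one scripted question, a short record form for therapists, and a few sentences of analysis text. No visit or treatment changes. Call data are self-reported. The gain also depends on reaching people: a relapser who stops answering would be censored closer to the relapse, where the simulation gives 0.73-0.79 rather than 0.71-0.74. The sensitivity analysis is there to show how far that could matter.

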## CPT-C Post Follow-Up

In order to ensure that all participants have access to evidence-based treatment for PTSD, all participants who were randomized to participate in the smoking cessation without concurrent CPT-C group will be offered the option of receiving 12 sessions of CPT-C following the 6-month follow-up session (i.e., session 15). Treatment will be provided by the same group of therapists who provided CPT-C in the smoking cessation + concurrent CPT-C group. Participants will not be provided smoking cessation counseling during these sessions, and smoking cessation medications will not be provided. In addition, participants will not be paid for participating in these study visits, as they have been previously paid to participate in smoking cessation counseling visits. Participants can choose not to participate in this portion of the study. Any participant who is offered and choose this treatment will continue to complete the PCL and BDI at each visit, as is consistent with CPT-C provided in a clinical setting. No other study measures will be required. Adverse event monitoring, data security, and other risk protections will continue during this portion of the study for those participants.

During this study, it is anticipated that participants will miss scheduled appointments, either through cancellation or no-shows. This does not necessarily constitute a protocol deviation. If a no-show or a missed appointment causes interruption in study activities (such as more than 2 days of missed medications), we will report the missed appointments to the IRB as protocol deviations. Otherwise, the missed appointments will be recorded in electronic study log books as necessary. Also, throughout the study, study staff may contact enrolled participants regarding study-related concerns, scheduling/rescheduling appointments, or appointment reminders.

# **Data Analysis and Hypotheses:**

The following variables will be described for the sample as a whole: minority status, marital status, age, trauma exposure, negative affect level, PTSD symptom severity, nicotine dependence, mean pack years, nicotine cigarette brand, and mean number of cigarettes smoked daily.

Because one of the aims of this study is to assess the efficacy of the combined CPT-C and smoking intervention on smoking cessation, we will analyze these variables to determine whether they change over time.

- Compared to the smoking cessation alone protocol, the smoking cessation + concurrent CPT-C protocol will result in reduced frequency and intensity of PTSD symptoms.
- Compared to the smoking cessation alone protocol, the smoking cessation + concurrent CPT-C protocol will result in reduced depressive symptoms.
- 3) The smoking cessation + concurrent CPT-C protocol will result in decreased smoking rates, relative to published data on VA smoking cessation usual care.
- 4) Greater PTSD symptom reduction during the smoking cessation + concurrent CPT-C treatment will result in longer duration to smoking lapse and relapse.
- 5) Exploratory research question: Will use of automated text messaging as an adjunct to smoking cessation be feasible, and will it impact quit rates and symptom severity?

Hypothesis 1. Compared to the PTSD Coach and smoking cessation protocol, the CPT-C and smoking cessation protocol will result in reduced frequency and intensity of PTSD symptoms. The change in PTSD symptoms over time will be analyzed using repeated-measures ANOVA, utilizing data provided at baseline, post-treatment, and 6-months post-quit. We will evaluate the potential influence of several potential psychosocial covariates on smoking abstinence, including: 1) demographics (age, race, socioeconomic

status), 2) psychiatric variables (PTSD symptom severity, depression, substance abuse/dependence), 3) smoking variables (self-efficacy, motivation to quit, social support, smokers in social group), and 4) treatment process variables (therapeutic alliance, satisfaction with treatment, attendance at sessions, homework adherence).

Hypothesis 2. Compared to the PTSD Coach and smoking cessation protocol, the CPT-C and smoking cessation protocol will result in reduced depressive symptoms. Analysis procedures for Hypothesis 2 will be the same as those used for Hypothesis 1.

Hypothesis 3. The CPT-C and smoking cessation protocol will result in decreased smoking rates, relative to published data on VA smoking cessation usual care. An outcome variable denoting the proportion of subjects abstinent at Week-6 will be regressed on the group proxy and included covariates using standard logistic regression procedures. A secondary analysis will explore cessation rates at the 6-month follow-up.

Hypothesis 4.-The level of PTSD symptom reduction during the intervention will be related to longer latency to relapse. PTSD symptom change scores will be used to evaluate the degree of PTSD symptom reduction. We will fit Cox proportional hazard regression models to the data to evaluate effects of PTSD symptom reduction on the time to relapse.

Hypothesis 5. Exploratory research question: Will use of automated text messaging as an adjunct to smoking cessation be feasible, and will it impact quit rates and symptom severity? This will be evaluated by examining proportion of participants choosing to utilize text messaging, retention rates, and usage rates.

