As recommended by Dillman, Smith, and Christian (Dillman, Smyth, & Christian, 2009), we will recruit participants by sending a series of four letters to those veterans who are smokers with PTSD who are registered at the Durham VA Medical Center. Based on social exchange theory, Dillman and colleagues recommend that the second letter be sent with a small token of appreciation. This token incentive serves two functions – it will encourage respondents to respond based on the principles of social exchange theory, and more importantly, it will bring additional attention to the request for participation so that it will be more readily considered. As recommended, letter two will be sent with a small selection (i.e., monetary value less than \$2) of commemorative stamps. After participants have received the second letter describing the study in detail, a study coordinator may contact them about participation. This information is included in letter 2. Only veterans who are identified via the VA's Fileman system or the MIRECC repository will be sent letters described above. Study staff members will perform random spot-checks of names and addresses on 50% of all letters prior to mailing. This will capture any sorting error that may have occurred during the preparatory procedures. Any person who contacts the study coordinator for more information about the study (whether it be through flyers, word of mouth, etc.) will be informed about the study using the IRB-approved telephone screen script. Participants who drop out will receive partial reimbursement for the time they donate. Participants will be paid up to \$545 for their complete participation. Study costs will be paid using funds from [name] Sciences Research & Development (CSR&D) Career Development Award. Screening is completed following the endorsement of informed consent and HIPAA form by the participant.

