## **Population**

The proposed study will recruit seventy male and female veterans ages 18 to 75 for participation in the CPT-C and smoking cessation treatment. Based on data from other similar clinical trials run in the Traumatic Stress and Health Research Laboratory, we estimate that we will need to recruit 120 participants in order to reach an enrollment goal of at least fifty participants.

Participants will be screened for good health by the study physician. If any participant indicates a medical problem that is a possible contraindication to nicotine replacement therapy (NRT), medical clearance to participate in the study will be obtained from their primary care provider and/or other treating physician (e.g. psychiatrist). If the request is denied or not returned, potential participants will be excluded from the study. We are seeking medical clearance rather than excluding participants based on self-report to ensure that we are not prematurely ruling out participants who may be eligible. We are consulting with their primary physician to determine if the use of NRT is appropriate and safe given their current physical status and medication regimen. This medical consult is

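### The three-visit repeated-measures ANOVA for Hypotheses 1 and 2 uses baseline only as a repeated outcome and has no missing-outcome rule; adjusting for the baseline score is a cheap gain in precision

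*Combined protocol and SAP*

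**What the plan says.** All of this is in the combined protocol and SAP, mostly under Data Analysis and Hypotheses.

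- **Comparison.** Hypotheses 1 and 2 are arm comparisons. The bulleted list names the comparator as smoking cessation alone. The paragraphs that give the analysis begin "Compared to the PTSD Coach and smoking cessation protocol", an arm described nowhere else in the document.
- **Method.** For Hypothesis 1: "The change in PTSD symptoms over time will be analyzed using repeated-measures ANOVA, utilizing data provided at baseline, post-treatment, and 6-months post-quit". For Hypothesis 2: "Analysis procedures for Hypothesis 2 will be the same as those used for Hypothesis 1".
- **Covariates.** The list in the Hypothesis 1 paragraph, which includes PTSD severity and depression, is introduced by "We will evaluate the potential influence of several potential psychosocial covariates on smoking abstinence". It is not tied to the symptom scores.
- **Missing outcomes.** The analysis section has no rule. CPT-C Post Follow-Up says "it is anticipated that participants will miss scheduled appointments, either through cancellation or no-shows", but deals only with deviation reporting and logging. Recruitment says "Participants who drop out will receive partial reimbursement for the time they donate".
- **Size.** Population gives seventy participants, and also a plan to "reach an enrollment goal of at least fifty participants".
- **Instrument.** Hypothesis 1 names none. Screening Session assigns PTSD severity to the PCL, while the three visits match the CAPS schedule (screening, sessions 14 and 15).

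**The concern.** These two hypotheses are the symptom comparisons that rest on randomisation, in a trial of 50 to 70 people, so precision matters.

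In a repeated-measures ANOVA with baseline as one of the outcomes, the arm comparison is a comparison of changes. That removes a chance baseline imbalance, but it subtracts the whole baseline score whatever its correlation with follow-up. Regression on baseline subtracts only the part that predicts follow-up, and so has smaller variance whenever the correlation is below 1.

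In its conventional form this ANOVA also drops anyone missing one of the three visits. The plan does not say that it will, but nor does it give any other rule.

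**Working it through.** The plan has no power figure to reproduce. It gives no effect size, SD, correlation, alpha, allocation ratio or dropout rate.

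**Assumptions.** 1:1 allocation, n = 25 or 35 per arm (totals of 50 and 70, from Population), two-sided 5%, unit SD, and the same correlation r = 0.5 to 0.7 between any two of the three measurements.

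**Step 1. Variance per participant, complete data.**

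| Contrast | Change score | Baseline-adjusted | Ratio | r = 0.5, 0.6, 0.7 |
|---|---|---|---|---|
| One follow-up visit | 2(1−r) | 1−r² | (1+r)/2 | 0.75, 0.80, 0.85 |
| Mean of two follow-ups | 3(1−r)/2 | (1−r)(1+2r)/2 | (1+2r)/3 | 0.67, 0.73, 0.80 |

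The ratios do not depend on the size or pattern of the effect.

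**Step 2. Power on the same contrast at d = 0.5 at both visits.** The standard error is √(2v/n), with v from Step 1. Power is from the noncentral t on 2n−2 df (change score) or 2n−3 df (adjusted).

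| N | r | One visit: change → adjusted | Mean: change → adjusted |
|---|---|---|---|
| 50 | 0.5 | 41% → 52% | 52% → 69% |
| 50 | 0.7 | 61% → 68% | 73% → 82% |
| 70 | 0.5 | 54% → 66% | 66% → 83% |
| 70 | 0.7 | 76% → 82% | 87% → 93% |

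The gain is about 6 to 12 points for one visit and 6 to 17 for the mean.

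**Step 3. Separating the sources of gain over the 2-df test.** Take d = 0.5 at both visits and r = 0.5. The arm differences are (0, 0.5, 0.5), and their squared deviations from the mean sum to 1/6. The noncentrality is (n/2)(1/6)/(1−r), which is 4.17 or 5.83. On 2 and 2(2n−2) df, the group-by-time power is 42% (N = 50) or 56% (N = 70). Moving to a 1-df change contrast on the follow-up mean gives 52% or 66%. Adding the baseline covariate gives 69% or 83%. Of the 27 points, about 10 come from choosing a contrast and about 17 from baseline.

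**Step 4. What the likelihood model adds.** This was simulated with d = 0.7 then 0.5 and r = 0.5. Random loss was 20% before post-treatment and 15% of the remainder before 6 months, so 1 − 0.80 × 0.85 = 32% are incomplete.

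| Analysis | N = 50 | N = 70 |
|---|---|---|
| Group-by-time ANOVA, completers | 43% | 58% |
| ANCOVA at post-treatment, everyone with that score | 69–71% | 83% |
| Likelihood model, post-treatment | 68% | 83% |
| ANCOVA of follow-up mean, completers | 65% | 80% |
| Likelihood model, follow-up mean | 69% | 84% |

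At post-treatment the model adds nothing beyond ANCOVA. Under this dropout everyone seen at 6 months also has a post-treatment score, so the later visit carries no extra information. For the mean it adds about 4 points.

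**Step 5. Contrasts that lose power.** Simulations crossed four effect patterns, r = 0.5 to 0.7, dropout from none to the Step 4 level, and both sample sizes (72 settings). The difference from the 2-df ANOVA ran from −10 to +28 points for the follow-up mean, −16 to +26 for post-treatment, and −72 to +20 for 6 months alone. The losses occur when the chosen contrast does not match the effect pattern.

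**The case against.** A reader might infer from "we will analyze these variables to determine whether they change over time" and from the ANOVA sentence that no arm comparison will be tested, or that the test is left open until the data are seen. The documents do not support that. The sentence immediately before the ANOVA states the comparison, and method and visits are named. A group-by-time test is the ordinary reading; the exact term or contrast is unstated rather than excluded.

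A reader might also take the full gap between 42% and 69% as power thrown away. It is not. Part of it reflects a directed 1-df question in place of an any-difference question. With no expected effect pattern in the documents, the omnibus test is defensible.

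Nor is heavy loss of data established. Expected missed appointments are not the same as lost outcome assessments. The plan allows for rescheduling and a no-contact letter, and its Background describes the 12-session protocol as having relatively low dropout. Listwise deletion is a convention of the method, not something the plan states. The 32% in Step 4 is an assumption.

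What stands against these objections is the same-contrast result. It needs no dropout and no favourable choice of contrast, and it uses a score that every participant already provides at screening.

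**Conclusion.** The point holds as a cheap improvement. Hypotheses 1 and 2 would be analysed more precisely with the baseline score as a covariate, and the plan needs a rule for participants with only one follow-up. Nearly all the same-contrast gain comes from the baseline covariate: 15 to 25% less variance for one visit and 20 to 33% less for the follow-up mean, at r = 0.5 to 0.7. The likelihood model itself is a modest addition, and the inference that it is the main source of the gain is not supported.

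The variance ratios assume complete data and equal correlations. The power figures also rest on the assumed d, 1:1 allocation and, in Step 4, completely random dropout. The comparator label and the unnamed instrument are details to tidy in the same edit, not separate faults of method.

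**What to change.** 1. Analyse each symptom outcome with its own baseline score as a covariate, in a likelihood-based repeated-measures model of the two follow-ups: arm, visit, arm-by-visit, unstructured covariance. Include participants with only one follow-up. If post-treatment is the chosen visit, a plain ANCOVA of everyone with that score is nearly as good.
2. Name the between-arm contrast before outcomes are seen by arm: post-treatment, the mean of the two follow-ups, or a joint test of both visits if no effect pattern is expected.
3. Correct the PTSD Coach label to the arm actually randomised, and name the instrument for Hypothesis 1.
4. State how missing outcomes are handled, preferably with a sensitivity analysis for departures from missing at random.

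The cost is SAP wording and slightly more modelling, with no new visits or data. The model relies on a missing-at-random assumption, and a 1-df contrast that does not match the true effect pattern can have less power than the 2-df test.
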